10.5 Analysis Time Points

10.5.1 Final Analysis

The final analysis of the study will occur 6 months after the last patient has been recruited into the study.

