Appendix F B: Schedule of Assessments – Cohort 2-SIR-Spheres then Regorafenib (continued)

^pPatients will be assessed at Screening (**4-7 days prior to SIR-Spheres treatment**) to determine the suitability for SIR-Spheres (see Section 7.2).

^f If ~~LFTs~~ **liver function toxicities** are present after a 2 week rest, then patients ~~may~~ **must** be rechecked weekly for 2 additional weeks **prior to Regorafenib treatment on C2D1**.

^h Biomarker samples (see Section 5.4) will be collected ~~prior to SIR-Spheres administration on Day 1, Day 8, and Day 30 (pre-dose) following SIR-Spheres treatment~~ from all patients prior to the hepatic angiogram and ^{99m}Tc MAA lung shunt scan, which will be obtained 7-4 days prior to SIR-Spheres treatment [see Section 7.2]), on Day 8 after SIR-Spheres radiation, and Day 30 (pre-dose) after SIR-Spheres radiation.

^p **Blood pressure is required Cycle 3 Day 8. Cycle 4 and beyond, blood pressure will be required Day 1 only.**

CONFIDENTIAL

STUDY DEVICE: SIR-Spheres®

SCRI INNOVATIONS STUDY NUMBER: GI 189

DATE OF ORIGINAL PROTOCOL: 16 December 2013

Date of Amendment #1: 15 April 2014

Version 2.0

GI 189 PROTOCOL SYNOPSIS

Title of Study:	A Two Arm Safety Study of Regorafenib before or after SIR-Spheres® Microspheres (⁹⁰ Y) for the Treatment of Patients with Refractory Metastatic Colorectal Cancer and Liver Metastases
SCRI Innovations Study Number:	GI 189
Sponsor:	SCRI Development Innovations, LLC
Study Duration:	The total duration of the study is planned to be 16 months. Phase of Study: II
Study Centers:	This study will be conducted at approximately 5 sites in the United States in the SCRI network.
Number of Patients:	Up to 50 patients are planned to be enrolled in this study.

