5. STUDY DESIGN

This is an open-label study comparing the safety of two treatment cohorts in which radioembolization will be administered using the device SIR-Spheres in combination with regorafenib to patients with mCRC with liver metastases. The two treatment cohorts will be evaluated for safety, ORR, PFS, and OS. Twenty-five patients will be treated in each cohort. The first cohort will complete enrollment before the second cohort opens. There will be no randomization or blinding.

A safety review for toxicity by the Medical Monitor will occur after the first 10 patients have been enrolled in each cohort and treated with one cycle of regorafenib and SIR-spheres (combination therapy) to assess the frequency of \geq Grade 3 adverse events and all SAEs. Accrual will not be halted while the analysis is being conducted.

Stopping Rules Due to Toxicities of Combination Therapy

Stopping rules due to toxicities assessed as related to combination therapy by the Medical Monitor will be defined as follows:

CONFIDENTIAL

STUDY DEVICE: SIR-Spheres®

SCRI INNOVATIONS STUDY NUMBER: GI 189

DATE OF ORIGINAL PROTOCOL: 16 December 2013

Date of Amendment #1: 15 April 2014

Version 2.0

- A patient death considered to be caused by AEs of combination therapy
- A patient with Grade 4 AST, ALT, or irreversible hepatic failure assessed as related to combination therapy;
- More than 2 patients that develop Grade 3 AST, ALT, or total bilirubin assessed as related to combination therapy;
- More than 2 patients develop Grade 3 bleeding in the lung, stomach, small intestine, or liver assessed as related to combination therapy.

If the early stopping rules are met or safety signals emerge from the group of the first 10 patients treated with combination therapy in each cohort, patient recruitment will discontinue and the study will be reassessed. Any outcome of these safety reviews will be communicated in a timely manner to the participating investigators so that they may notify their IRBs.

Blood samples will be collected from all patients prior to the hepatic angiogram and ^{99m}Tc MAA lung shunt scan, on Day 8 after SIR-Spheres treatment, and Day 30 (pre-dose) after SIR-Spheres treatment (see Section 5.1). Expressions of cytokines and proteins will be measured to explore potential biomarkers that may correlate with clinical outcome. The study schema is presented in Figure 1.

CONFIDENTIAL

STUDY DEVICE: SIR-Spheres®

SCRI INNOVATIONS STUDY NUMBER: GI 189

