7.7 Follow-Up

7.7.1 Follow-up for Patients Who Discontinue Prior to Disease Progression

Patients discontinuing treatment for any reason other than PD will be monitored for evidence of disease progression. Patients will be followed every 3 months (± 1 month) for up to a maximum of 6 months after the last patient has been enrolled on study for disease progression. Assessments at these visits will be performed as described in Appendix A **Error! Reference source not found.** and Appendix B **Error! Reference source not found.**

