7.7.2 Survival Follow-Up

After disease progression is documented, patients will be followed every 3 months (± 1 month) for survival (e.g., date and cause of death) for up to a maximum of 6 months after the last patient has enrolled on study or death whichever comes first. Patients may be contacted during outpatient visits or by telephone.

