10. STATISTICAL CONSIDERATIONS

10.1 Statistical Design

The safety of two treatment cohorts will be evaluated in this open-label study. The administration sequence of radioembolization with SIR-Spheres and regorafenib is different in the two treatment cohorts. The treatment cohorts are:

Cohort 1 Regorafenib (one cycle) followed by SIR-Spheres followed by re-initiation of regorafenib 2-4 weeks after SIR-Spheres

Cohort 2 SIR-Spheres followed by regorafenib to start 2-4 weeks after SIR-Spheres

Enrollment to Cohort 1 will be completed before Cohort 2 begins enrolling patients. All patients will take regorafenib, orally once-a-day, on Days 1-21 of a 28-day treatment cycle. Twenty-five patients will be treated in each cohort.

Primary Objective

The primary objective of the study is to evaluate the safety of two treatment cohorts combining regorafenib and SIR-Spheres in patients with refractory mCRC with liver metastasis.

Secondary Objectives

The secondary objectives of the study are to evaluate the overall response rate (ORR), progression free survival (PFS), and OS of patients with refractory mCRC when treated with combination SIR-Spheres and regorafenib in the two sequencing cohorts.

Exploratory Objectives

The exploratory objectives will evaluate the status of biomarkers and correlate the clinical outcomes of patients treated in the two SIR-Spheres and regorafenib cohorts.

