 Early Progression Rate (EPR)			
 Time To Progression (TTP)	Default: Estimates of medians in each treatment arm		
 Progression-Free Survival (PFS)	 Other quartiles or percentages of survival required, specify: probability evaluated at 6 month intervals		
 Overall Survival (OS)	 Hazard ratio & 95% confidence interval between treatment arms, unstratified		
 Duration of Response	 p-value, specify statistical test:		
 Duration of Stable Disease	 Hazard ratio & 95% confidence interval between treatment arms, stratified (specify stratification factor(s)):		
 Time To Treatment Failure (TTF)	 p-value, specify statistical test:		
 Other, Specify:			
7 Safety			
Adverse Events	Definition of Treatment-Emergent Adverse Event (TEAE): any adverse event (AE) that starts or worsens after the start of the first dose of study treatment up to 30 days post last dose.		
Laboratory Data	Data will be summarized by:  NCI-CTCAE for CTCAE-gradable parameters, and H/L for non-CTCAE-Gradable parameter		

H/L for all lab parameters

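### Sequential cohorts share one calendar cut-off, so Cohort 1 always has the longer potential follow-up, and no common window is planned for side-by-side AE and survival results

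*Protocol*

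**What the plan says.** - **Order of enrolment.** Protocol section 5: "The first cohort will complete enrollment before the second cohort opens". Section 10.1 repeats it: "Enrollment to Cohort 1 will be completed before Cohort 2 begins enrolling patients". The target is 25 patients per cohort, without randomization.
- **One study-level end date.** Protocol section 10.5.1: "The final analysis of the study will occur 6 months after the last patient has been recruited into the study". SAP section 1.4 gives the same timing. Progression follow-up (protocol 7.7.1) runs "for up to a maximum of 6 months after the last patient has been enrolled on study for disease progression", and survival follow-up (7.7.2) runs "for up to a maximum of 6 months after the last patient has enrolled on study or death whichever comes first".
- **Planned length.** Protocol synopsis: "The total duration of the study is planned to be 16 months". No accrual rate or accrual period per cohort is stated.
- **What is reported.** For PFS and OS the SAP (section 5/6) asks for "probability evaluated at 6 month intervals". It also ticks a between-cohort difference in ORR with a confidence interval. Protocol 10.4.4 summarizes AEs as incidence by cohort, and SAP section 7 counts treatment-emergent AEs until 30 days after the last dose. Treatment is open-ended, to progression or intolerance (protocol 5.2).
- **What is absent.** Neither document sets a common observation window, a cut-off per cohort, or an exposure-adjusted AE rate. SAP Table 3 reports regorafenib treatment duration, but nothing links it to the AE percentages.

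**The concern.** Both documents describe the study as comparing the safety of the two sequences, and safety is the primary objective. The last patient recruited is in Cohort 2, so the single cut-off gives Cohort 1 additional calendar time equal to at least the part of Cohort 2's accrual that precedes each Cohort 2 patient's entry. Crude AE percentages placed side by side then reflect both the treatment sequence and the length of observation. Kaplan-Meier methods deal with unequal administrative censoring up to each cohort's last follow-up, but cannot supply a landmark that no patient in a cohort could reach. In a non-randomized, sequential design, calendar and selection differences cannot be removed. Unequal observation time is a source of non-comparability that can be.

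**Working it through.** **The plan's own figure.** The 16-month duration cannot be reproduced, because no accrual rate is given. It can only be split: 16 − 6 = 10 months of accrual in total.

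**Follow-up in general.** Let T1 and T2 be the accrual periods of Cohorts 1 and 2, in months. The cut falls at T1 + T2 + 6. Potential follow-up is then

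- Cohort 1: from 6 + T2 to 6 + T1 + T2
- Cohort 2: from 6 to 6 + T2

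The shortest Cohort 1 follow-up equals the longest in Cohort 2. This ordering needs no assumption about accrual.

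**Share able to reach 12 months.** With uniform entry, the share in Cohort 2 is max(0, (T2 − 6)/T2), which is zero only when T2 is 6 months or less.

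| T1 + T2 (assumed) | Cohort 1 follow-up | Cohort 2 follow-up | Reach 12 months, C1 vs C2 |
|---|---|---|---|
| 5 + 5 | 11–16 | 6–11 | 80% vs 0% |
| 4 + 6 | 12–16 | 6–12 | 100% vs 0% |
| 6 + 4 | 10–16 | 6–10 | 67% vs 0% |
| 3 + 7 | 13–16 | 6–13 | 100% vs 14% |
| 8 + 8 | 14–22 | 6–14 | 100% vs 25% |
| 10 + 10 | 16–26 | 6–16 | 100% vs 40% |
| 12 + 12 | 18–30 | 6–18 | 100% vs 50% |

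The first four rows fit the 16-month plan; the last three show slower accrual.

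**Effect on AE percentages (5 + 5).** Assume exponential time on treatment with median m, so λ = ln 2 / m, and a constant late-AE hazard h per month while on treatment. For follow-up T, expected incidence is h/(h + λ) × [1 − exp(−(h + λ)T)], averaged over uniform T on 11–16 or 6–11 months. The 1.9-month median is the regorafenib PFS in protocol section 1, used as a stand-in for time on treatment. The 4-month median and the hazards are assumptions. The 30-day tail after the last dose is ignored.

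| Median on treatment | h | Cohort 1 | Cohort 2 | Difference |
|---|---|---|---|---|
| 1.9 months | 0.05 | 12.0% | 11.6% | 0.4 points |
| 1.9 months | 0.10 | 21.5% | 21.0% | 0.5 points |
| 4 months | 0.05 | 21.2% | 18.9% | 2.4 points |
| 4 months | 0.10 | 35.6% | 32.7% | 2.9 points |

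Mean observed time on treatment, (1 − mean of exp(−λT))/λ, is 2.72 versus 2.60 months at a median of 1.9 (5% longer in Cohort 1) and 5.20 versus 4.41 months at a median of 4 (18% longer). One patient in 25 is 4 points.

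**Responses.** Scans fall at weeks 6 and 12 after SIR-Spheres and every 8 weeks after that (protocol 5.2, 7.5); confirmation needs 4 weeks. Cohort 1 receives SIR-Spheres about 4 weeks after Day 1. Counted from Day 1, the scans at post-SIR-Spheres weeks 6, 12 and 20 fall at about weeks 10, 16 and 24 in Cohort 1 and weeks 6, 12 and 20 in Cohort 2. Six months is about 26 weeks. Apart from delays, a response first seen by week 12 after SIR-Spheres can therefore be confirmed inside the minimum follow-up in both cohorts.

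**The case against.** The study is descriptive, with no formal hypothesis test, and the only between-cohort difference that the SAP ticks is for ORR. AE collection stops 30 days after the last dose and treatment stops at progression, so much of Cohort 1's extra calendar time is off treatment. The AE distortion computed above is less than one patient per cohort. Kaplan-Meier medians are not biased by administrative censoring alone, and a landmark that cannot be estimated is an empty cell, not a wrong number. All of this stands, and it limits the weight of the point. It does not remove it: the ordering of follow-up is structural, and the plan has nothing that makes the side-by-side AE figures comparable.

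Three stronger readings are tempting, and the documents do not support them.

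- A reader might infer that 12-month PFS and OS can be observed in Cohort 1 only, as a fixed feature of the design. That requires Cohort 2 to accrue in 6 months or less, which the 16-month plan implies under roughly even accrual but which is nowhere stated. The SAP is dated 22MAY2018, about four years after the April 2014 amendment, so slower accrual is possible; actual accrual dates are not given. The SAP also names no 12-month column; it follows only from the 6-month spacing.
- A reader might infer that Cohort 1's response rate is raised by construction. The scan schedule shows that only late first responses could differ.
- A reader might infer a material inflation of Cohort 1's AE percentages. At the protocol's own 1.9-month figure the difference is about half a point.

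**Conclusion.** The point holds in a limited form. Sequential enrolment with one calendar cut gives Cohort 1 at least as much potential follow-up as Cohort 2 under any accrual pattern, and the plan presents crude AE incidence and 6-monthly survival probabilities without a common window. Under 16 months and an assumed 5 + 5 split, follow-up is 11–16 versus 6–11 months and a 12-month landmark is reachable in Cohort 1 only; this changes once Cohort 2 accrual exceeds 6 months. The AE effect is 0.4–0.5 points at a 1.9-month median on treatment and 2–3 points at 4 months, assuming exponential times, uniform entry and late-AE hazards of 0.05–0.10 per month. Response rates and Kaplan-Meier medians are little affected. This is an inexpensive improvement to presentation and pre-specification, not a flaw that undermines the study.

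One reading could alter the windows. SAP section 5/6 describes follow-up assessment every 3 months up to 6 months without naming the starting point. If that is a limit per patient, it conflicts with protocol 7.7, which counts from the last enrolment.

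**What to change.** In SAP sections 5/6 and 7:

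1. Keep the all-data AE tables by cohort, and add patient-months at risk and exposure-adjusted rates.
2. Add one pre-specified side-by-side AE table over common windows, shown two ways: from first treatment up to 6 months, and from SIR-Spheres administration over a shorter window, for example 20 weeks. Both are needed. Cohort 1 has a 4-week regorafenib cycle first, so 6 months (about 26 weeks) from first treatment leaves it about 22 weeks after SIR-Spheres, against 26 in Cohort 2.
3. In the first window, censor and count any patient with less than 6 months. The 6 months run from recruitment, not first treatment, so the last patient may fall short. In the second, state how many patients received SIR-Spheres.
4. Show numbers at risk with every Kaplan-Meier probability. Compare cohorts side by side only at landmarks within both cohorts' follow-up, and report later ones by cohort as descriptive.
5. Reconcile the SAP's follow-up wording with protocol 7.7.1 and 7.7.2.

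The cost is some programming and a few table columns. Later Cohort 1 data drop out of the side-by-side columns but are still reported.

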11. SAFETY REPORTING AND ANALYSES

Safety assessments will consist of monitoring and recording protocol-defined AEs and Serious AEs (SAEs), measurement of protocol-specified hematology, clinical chemistry, and other protocol-specified tests that are deemed critical to the safety evaluation of the study drug.

CONFIDENTIAL

STUDY DEVICE: SIR-Spheres®

SCRI INNOVATIONS STUDY NUMBER: GI 189

DATE OF ORIGINAL PROTOCOL: 16 December 2013

Date of Amendment #1: 15 April 2014

Version 2.0

The Principal Investigator is responsible for recognizing and reporting AEs to the SCRI Innovations Safety Department (see Section 11.2). It is the Sponsor's responsibility to report relevant SAEs to the applicable local, national, or international regulatory bodies. In addition, Investigators must report SAEs and follow-up information to their responsible Institutional Review Board (IRB) according to the policies of that IRB.

The Principal Investigator is also responsible for ensuring that every staff member involved in the study is familiar with the content of this section.

11.1 Definitions

11.1.1 Adverse Events

Adverse event means any untoward medical occurrence associated with the use of a drug in humans, whether or not considered drug related. An adverse event (also known as adverse experience) can be any unfavorable and unintended sign (e.g., an abnormal laboratory finding), symptom, or disease temporarily associated with the use of a drug, without any judgement about causality. An adverse event can arise with any use of the drug (e.g., off-label use, use in combination with another drug) and with any route of administration, formulation, dose or including overdose.

11.1.2 Serious Adverse Event

An AE or a suspected adverse reaction (SAR) is considered “serious” if, in the view of either the investigator or sponsor, it results in any of the following outcomes:

- Death**
- A life-threatening AE (Note: the term “life-threatening” refers to an event/reaction in which the patient was at risk of death at the time of the event/reaction; it does not refer to an event/ reaction which hypothetically might have caused death if it were more severe)**
- Inpatient hospitalization or prolongation of existing hospitalization**
- A persistent or significant incapacity or substantial disruption of the ability to conduct normal life functions**
- A congenital anomaly/birth defect**

Important medical events that may not result in death, be life-threatening, or require hospitalization may be considered serious when, based upon appropriate medical judgment, they may jeopardize the patient or subject and may require medical or surgical intervention to prevent one of the outcomes listed in this definition. Examples of such medical events include allergic bronchospasm requiring intensive treatment in an emergency room or at home, blood dyscrasias or convulsions that do not result in hospitalization, or development of drug dependency or drug abuse.

It is important to distinguish between “serious” and “severe” AE, as the terms are not synonymous. Severity is a measure of intensity; however, an AE of severe intensity need not necessarily be considered serious. Seriousness serves as the guide for defining regulatory

CONFIDENTIAL

STUDY DEVICE: SIR-Spheres®

SCRI INNOVATIONS STUDY NUMBER: GI 189

DATE OF ORIGINAL PROTOCOL: 16 December 2013

Date of Amendment #1: 15 April 2014

Version 2.0

reporting obligations. “Serious” is a regulatory definition and is based on patient/event outcome or action usually associated with events that pose a threat to a patient’s life or vital functions. For example, nausea which persists for several hours may be considered severe nausea, but may not be considered an SAE. On the other hand, a stroke which results in only a limited degree of disability may be considered only a mild stroke, but would be considered an SAE. Severity and seriousness should be independently assessed when recording AEs on the eCRF and SAEs on the SAE Report Form.

11.1.3 Adverse Reaction

An adverse reaction means any adverse event caused by a drug. Adverse reactions are a subset of all suspected adverse reactions where there is a reason to conclude that the drug caused the event.

11.1.4 Suspected Adverse Reaction

Suspected adverse reaction means any adverse event for which there is a reasonable possibility that the drug caused the adverse event. Reasonable possibility means that there is evidence to suggest a causal relationship between the drug and the adverse event. A suspected adverse reaction implies a lesser degree of certainty about causality than adverse reaction, which means any adverse event caused by a drug.

11.1.5 Recording and Reporting of Adverse Events

Recording of Adverse Events

All AEs of any patient during the course of the research study will be recorded in the eCRF, and the investigator will give his or her opinion as to the relationship of the AE to the study material or process (i.e., whether the event is related or unrelated to study drug administration, SIR-Spheres microspheres or SIRT procedure).

All AEs should be documented. A description of the event, including its date of onset and resolution, whether it constitutes a serious adverse event (SAE) or not, any action taken (e.g., changes to study treatment), and outcome, should be provided, along with the investigator’s assessment of causality (i.e., the relationship to the study treatment[s]). For an AE to be a suspected treatment-related event there should be at least a reasonable possibility of a causal relationship between the protocol treatment and the AE. Adverse events will be graded according to the NCI CTCAE v4.0, and changes will be documented.

If the AE is serious, it should be reported immediately to SCRI Innovations Safety Department. Other untoward events occurring in the framework of a clinical study are to be recorded as AEs (i.e., AEs that occur prior to assignment of study treatment that are related to a protocol-mandated intervention, including invasive procedures such as biopsies, medication washout, or no treatment run-in).

Any clinically significant signs and symptoms; abnormal test findings; changes in physical examination; hypersensitivity; and other measurements that occur will be reported as an AE, and collected on the relevant eCRF screen.

CONFIDENTIAL

STUDY DEVICE: SIR-Spheres®

SCRI INNOVATIONS STUDY NUMBER: GI 189

DATE OF ORIGINAL PROTOCOL: 16 December 2013

Date of Amendment #1: 15 April 2014

Version 2.0

Test findings will be reported as an AE if: the test result requires an adjustment in the study drug(s) or discontinuation of treatment, and/ or test findings require additional testing or surgical intervention, a test result or finding is associated with accompanying symptoms, or a test result is considered to be an AE by the investigator.

CONFIDENTIAL

STUDY DEVICE: SIR-Spheres®

SCRI INNOVATIONS STUDY NUMBER: GI 189

DATE OF ORIGINAL PROTOCOL: 16 December 2013

Date of Amendment #1: 15 April 2014

Version 2.0

Reporting Period for Adverse Events

All AEs regardless of seriousness or relationship to regorafenib and/or SIR-Spheres treatment (called study treatment), spanning from the start of study treatment, until 30 calendar days after discontinuation or completion of study treatment as defined by the clinical study for that patient, are to be recorded on the corresponding screen(s) included in the eCRF.

All AEs resulting in discontinuation from the study should be followed until resolution or stabilization. All new AEs occurring during this period must be reported and followed until resolution unless, in the opinion of the investigator, the AE or laboratory abnormality/ies are not likely to improve because of the underlying disease. In this case, the investigators must record his or her reasoning for this decision in the patient's medical record and as a comment on the eCRF screen.

After 30 days of completion of protocol-specific treatment or discontinuation, only AEs, SAEs, or deaths assessed by the investigator as treatment related are to be reported.

